### 5.3.2 Methods of sample collection

#### 5.3.2.1 Plasma sampling for analysis of BI 409306 and metabolites

At Visit 2 blood samples of 3 mL each will be collected from each patient at pre-dose and at 2 post-dose sampling timepoints within the first 1.5 hours after drug intake. One additional blood sample of 3 mL will be collected from each patient at the end of Visit 2 only after all other scheduled procedures have been performed. See [Table 10.3:1](#).

The two metabolites CD 13896 and CD 14084 will be analysed if BI 409306 plasma concentration is BLQ (below the limit of quantification) in the trough samples from Visits 8 and 16, and, if BI 409306 plasma concentrations are above BLQ in two of the samples from Visit 2.

Detailed instructions for obtaining, handling and shipping PK samples are provided in the laboratory manual.

Special attention must be directed to exact timing and instant recording of plasma sampling and drug administration as well as to the correct handling, labelling and storage of samples. At Visit 2, the clock time of the administration of the first BI 409306 dose (during the study visit) and of the actual PK sampling times will be recorded in the eCRF.

At Visits 8 and 16, the clock time of the administration of the last BI 409306 dose (at home) and of the actual PK sampling times will be recorded in the eCRF.

### 5.3.4 Pharmacokinetic – pharmacodynamic relationship

The relationship between the BI 409306 plasma concentrations and efficacy response and AE may be assessed descriptively.

## 5.4 ASSESSMENT OF BIOMARKER(S)

### 5.4.1 Biobanking

Participation in sampling for biobanking (including DNA) is voluntary and not a prerequisite for participation in the trial. A sample for DNA biobanking will be taken only after a separate biobanking informed consent has been given in accordance with local ethical and regulatory requirements. Banked samples may be analysed in the future for scientific evaluations or to further, for example, the mechanistic understanding of drug effects and/or to identify genetic or other factors associated with response to therapy or the risk of adverse drug reactions. Measures are in place to comply with the applicable rules for the collection, biobanking and future use of biological samples and clinical data, in particular

- Sample and data usage has to be in accordance with the separate biobanking informed consent.
- The BI-internal facilities storing biological samples from clinical trial participants as well as the external banking facility are qualified for the storage of biological samples collected in clinical trials.
- An appropriate sample and data management system, including audit trail for clinical data and samples to identify and destroy such samples according to the informed consent form (ICF) is in place
- A fit for the purpose documentation (biomarker proposal, analysis plan and report) ensures compliant usage
- A fit for purpose approach will be used for assay/equipment validation depending on the intended use of the biomarker data
- Samples and/or data may be transferred to third parties and other countries as specified in the biobanking ICF

#### 5.4.1.1 Methods and Timing of Pharmacogenomic Sample Collection

Sampling will be performed at the time points specified in the [Flow Chart](#). Approximately 8.5 mL of blood will be drawn into a PAXgene Blood DNA tube, preferably at Visit 2. If not feasible at Visit 2, the sample can also be taken at a later visit during the treatment period.

Detailed instructions on sampling, preparation, processing, shipment and storage are provided in the laboratory manual. DNA, extracted from the original whole blood sample, will be stored at the Sponsor.

### 5.4.2 Pre-specified Pharmacogenomic Analysis

[figure not shown]
One blood sample will be taken at the screening visit for genotyping of CYP2C19 from all patients taking medication known to be strong or moderate inhibitors of CYP1A2. Patients classified as poor metabolizers (poor metabolizers defined as presence of two non-functional

alleles (\*2 and \*3) of the CYP2C19 gene) may be excluded from enrollment (see [Section 3.3.3](#) (Exclusion criteria) and [Section 4.2.2.1](#) (Restrictions regarding concomitant treatment)).

In addition, all randomised patients will be asked for one mandatory blood sample for pre-specified pharmacogenomic analyses at Visit 2. If not feasible at Visit 2, the sample can also be taken at a later visit during the treatment period. In case of a positive study outcome, the sample may be used for DNA extraction and subsequent genotyping for variants in genes involved in absorption, distribution, metabolism and elimination of the compound. It is not intended to include these data in the final report. However, the data may be part of the report if necessary.

All remaining samples will be destroyed no later than two years after the end of the trial.

Detailed instructions on sampling, preparation, processing, shipment and storage of the samples are provided in the laboratory manual.

## 5.6 APPROPRIATENESS OF MEASUREMENTS

All measurements performed during this trial are acceptable measurements and commonly used in monitoring safety aspects or assessing treatment response in patients meeting diagnostic criteria for schizophrenia.

The scheduled measurements are appropriate to see drug induced changes in physical examination, vital signs, ECG and standard laboratory values. The primary and secondary efficacy endpoints and safety endpoints are standard and accepted for evaluation of safety and tolerability of an oral drug.

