### Clinical Summary

In all 12 healthy volunteer trials, the most frequent drug related adverse events were visual side effects that occurred shortly after dosing, mostly resolved within 1 h, i.e., in close

connection to maximum BI 409306 plasma concentrations, as the concentration-time profile sharply and steeply peaks within the first 1-2 hours and then rapidly declines afterwards. Overall, there were no relevant changes observed for laboratory, electrocardiogram (ECG) recordings, and vital signs following treatment with BI 409306 when compared to placebo. Only a rapid and short lasting increase in supine pulse rate of  $12.5 \pm 2.7$  beats per minute (bpm) was reported in Chinese CYP2C19 poor metabolizers subjects treated with BI 409306 (100 mg single dose) in study 1289.4. Following this observation, pharmacometric analysis of all available human data revealed a BI 409306 plasma concentration dependent increase in supine pulse rate in typical subjects reaching a maximum of 7-13 bpm (median) at the high exposure end in CYP2C19 poor metabolizers treated with BI 409306 at 100 mg. The maximum effects of BI 409306 on pulse rate were generally achieved at maximum BI 409306 plasma concentrations (20-30 minutes post dose) and disappeared rapidly with declining concentrations [[c01694347-09](#)]. The effects of BI 409306 on pulse rate were further examined in healthy male volunteers under resting and exercise conditions following single oral doses of 50 and 200 mg [[c03808525-01](#)]. In line with previous results, heart rate profiles closely correlated with drug systemic exposure profiles and the heart rate increase was 11.51 bpm at the maximum individual plasma concentration measured during exercise.

Altogether, good to satisfactory safety and tolerability were observed in single doses of BI 409306 (up to 350mg in CYP2C19 extensive metabolizers (EM); up to 100mg in CYP2C19 poor metabolizers (PM)) in healthy young volunteers and multiple doses (14 days up to 100mg EM/50mg PM) of BI 409306 in healthy young and elderly subjects. In addition data from completed studies demonstrate that the increase in heart rate was transient, closely related to the time of maximum drug concentrations, and of low amplitude [[c01694347-09](#)].

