Day 7 1 tablet in P.M.	1 x 10 mg placebo tablet	1 x 10 mg placebo tablet	1 x 10 mg BI 409306 tablet	1 x 10 mg placebo tablet	1 x 10 mg BI 409306 tablet

Administration of study drug tablets will be in the evening, preferably just before going to bed. The most common side effects with the use of BI 409306 are visual adverse events occurring at maximum concentration ( $C_{max}$ ) (30-40 min post-dose). By taking the study drug at bedtime, the negative effect, if any, of experiencing these side effects is expected to be minimized.

Patients should be instructed to take their study medication with water at approximately the same time in the evening, with or without food. BI 409306 tablets should not be chewed or crushed. If a dose is missed by more than 12 hours, that dose should be skipped and the next dose should be taken as scheduled.

A dose reduction of BI 409306 is not possible.

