## 6.2.2 Treatment period(s)

Eligible patients will be trained and set-up with the smartphone medication adherence monitoring Platform at Visit 2 prior to taking their first dose of study drug. Please refer to the manual in the ISF.

Study medication will be allocated via IRT and dispensed at visits specified in the [Flow Chart](#). Patients will be assigned a new medication number(s) at each of these visits. The first dose of study drug will be administered at the site after all baseline assessments have been completed and trial eligibility confirmed at Visit 2.

See Sections [5.3.2](#) and Section [10.3](#) for the sampling methods and time schedule for PK blood sampling.

Phone Visits are to be conducted at the time points specified in the [Flow Chart](#) to assess the overall status of the patient, assess suicidality, check compliance, and to collect new AE and concomitant medication information. If symptom worsening is suspected, an unscheduled in-clinic visit should be scheduled to further assess the patient for relapse. During the unscheduled visit, information should be gathered to determine whether any criteria for relapse have been met. PANSS and CGI-S should be assessed, as well as any other assessments necessary to assess the patient's condition, in the judgment of the investigator.

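### No vital-sign or ECG assessment is scheduled at or near peak concentration, so the schedule says little about the transient pulse-rate effect, and Sections 5.6 and 1.4 are worded too broadly

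*Protocol*

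**What the plan says.** **The claim for the schedule.** Protocol Section 5.6 says: "The scheduled measurements are appropriate to see drug induced changes in physical examination, vital signs, ECG and standard laboratory values". Section 1.4 relies on the Flow Chart for monitoring cardiac function.

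**The known effect.** Section 1.2 (Clinical Summary) describes a concentration-dependent rise in supine pulse rate. The largest effects came at "maximum BI 409306 plasma concentrations (20-30 minutes post dose) and disappeared rapidly with declining concentrations". Section 4.1.4 puts Cmax slightly later, at 30-40 minutes.

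**Dosing.** Section 4.1.4: "Administration of study drug tablets will be in the evening, preferably just before going to bed". Section 5.3.2.1 confirms that the last dose before Visits 8 and 16 is taken at home. The exception is Visit 2, where Section 6.2.2 says: "The first dose of study drug will be administered at the site after all baseline assessments have been completed".

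**Readings.** The Flow Chart marks vital signs once at Visit 2, at the later clinic visits, and at Visits 17 to 19. It marks ECGs at Visits 1, 8 and 16 and in a closing column, with none at Visit 2. Section 5.2.2 sets only a five-minute seated rest. Flow Chart footnote 8 lets the ECG be done up to 24 hours before the visit. None of these ties a reading to dose time.

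**PK samples.** These are tied to the dose. At Visit 2 there are "2 post-dose sampling timepoints within the first 1.5 hours after drug intake", and Table 10.3: 1 gives them as 0:45 (window 15 minutes to 1:00 h) and 1:30, with a further sample after 2 hours. At Visits 8 and 16 the window is 8-24 hours.

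**SAP.** Section 6.7 uses Visit 1 as the vital-signs baseline. Section 7.8.3 keeps the latest reading when there are several in one visit window.

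**The concern.** The protocol describes one cardiovascular effect in humans, gives its timing to within minutes, and then schedules no pulse, blood-pressure or ECG reading at that time. The chance exists: at Visit 2 the patient takes a supervised dose and stays more than two hours for timed blood draws, but no pulse reading is paired with those draws.

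At stake is what the vital-sign and ECG tables can be said to show. They can inform on changes that persist to the clinic visit, and on the withdrawal/taper week. If they are reported under the general statement in Section 5.6, nothing tells the reader that they hold almost no information on the peak effect in patients taking antipsychotics. That includes CYP2C19 poor metabolisers who take no CYP1A2 inhibitor: exclusion criterion 13 does not exclude them, and Section 5.4.2 does not genotype them at screening.

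**Working it through.** The plan states no figure for this point, so there is none to reproduce. The check compares times.

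**Step 1. Time of each reading against time of peak**

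| Reading | Time from last dose | Source |
|---|---|---|
| Peak pulse effect | 20-30 min | Protocol 1.2 |
| Cmax, second statement | 30-40 min | Protocol 4.1.4 |
| Visit 2 vital signs | no clock time; pre-dose if they count as baseline assessments | Flow Chart, 6.2.2 |
| Visit 2 ECG | none | Flow Chart |
| Visits 8 and 16, vital signs and ECG | 8-24 h if taken with the PK sample | Flow Chart, Table 10.3: 1 |
| Other clinic visits, vital signs | not written; many hours, inferred from bedtime dosing | Flow Chart, 4.1.4 |

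The earliest PK time at Visits 8 and 16 is 8 h. Against the stated peaks: 8 / (20/60) = 24; 8 / (30/60) = 16; 8 / (40/60) = 12. The window therefore opens 12 to 24 times later than the peak. Section 5.3.2.1 itself treats these samples as troughs and plans for values below the limit of quantification.

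**Step 2. What might remain at those times (illustration)**

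The documents give no half-life and no standard deviation. Assumptions: effect proportional to concentration; peak at 0.5 h; half-life h between 0.5 and 3 h; SD 10 bpm. The starting value of 12.5 bpm is the Section 1.2 figure for poor metabolisers at 100 mg. It is not an estimate for this trial.

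Residual at time t = 12.5 × 2^(−(t − 0.5)/h). The standard error for one visit at the planned size is 10 × √(1/129 + 1/258) = 1.08 bpm. Power = Φ(residual/1.08 − 1.96).

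| h | Residual at 8 h (power) | Residual at 12 h (power) | Residual at 24 h |
|---|---|---|---|
| 0.5 h | 0.0 bpm (about 3%) | 0.0 bpm (about 3%) | 0.0 bpm |
| 1 h | 0.07 bpm (3%) | 0.004 bpm (about 3%) | 0.0 bpm |
| 2 h | 0.9 bpm (14%) | 0.2 bpm (4%) | 0.004 bpm |
| 3 h | 2.2 bpm (54%) | 0.9 bpm (13%) | 0.06 bpm |

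Power at the peak itself would be about 100%. Averaging visits would raise precision, and the reduced sample lowers it. The result depends heavily on the half-life: at 3 h and the early edge of the window, a sizeable residual could still be detected.

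**Step 3. What a Visit 2 reading would capture**

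Under the same formula, at 0:45 (t = 0.75) the residual is 12.5 × 2^(−0.25/0.5) = 8.8 bpm for h = 0.5, and 12.5 × 2^(−0.25/3) = 11.8 bpm for h = 3. At 1:30 (t = 1.5) it is 12.5 × 2^(−1/0.5) = 3.1 bpm and 12.5 × 2^(−1/3) = 9.9 bpm. The 0:45 draw is the useful one, and its window covers both stated peak times.

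**The case against.** **The peak effect has already been studied.** Section 1.4 reports a dedicated cardiovascular study with no clinically relevant impact on heart rate or cardiac function. Section 1.2 calls the rise transient and of low amplitude, and reports good to satisfactory tolerability with multiple doses up to 50 mg in poor metabolisers. This stands and limits the weight of the point. The cardiac study used single doses in healthy men, so it does not make the present schedule informative about peak effects in treated patients.

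**The published sizes do not transfer.** Section 1.2 describes the modelled effect as "reaching a maximum of 7-13 bpm (median) at the high exposure end in CYP2C19 poor metabolizers treated with BI 409306 at 100 mg". From the study of single 50 and 200 mg doses at rest and on exercise it reports that "the heart rate increase was 11.51 bpm at the maximum individual plasma concentration measured during exercise". A reader might infer a rise of about 12 bpm in this trial. The documents give no resting figure at 25 or 50 mg, so that inference is not supported.

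**The timing is partly inferred.** The pre-dose position of Visit 2 vital signs follows from Section 6.2.2, but the Flow Chart gives no clock time, the SAP baseline is Visit 1, and Section 5.3.2.1 takes the last PK sample after all other procedures, so some may follow the dose. The 8-24 h window is written for PK at Visits 8 and 16 only. ECGs up to 24 hours early, and doses up to 12 hours late, make a near-peak reading possible by chance. All of this stands: the supportable statement is that no reading is placed near peak by design.

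**Section 5.6 is a general statement.** It does not name the pulse effect, and clinic readings can detect lasting changes. So the sentence is too broad rather than false.

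**Conclusion.** The point holds as a limited one. No vital sign or ECG is scheduled at or near peak concentration, including after the supervised dose at Visit 2. The scheduled data can show persistent changes but say little about an effect that peaks at 20-30 minutes and fades quickly, and Sections 5.6 and 1.4 should say so.

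The gap in time (8 h against 20-40 minutes) comes from the documents. The loss of signal is illustrative and rests on an assumed half-life, an SD of 10 bpm and proportionality to concentration. The size of the effect at the trial doses is unknown.

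Three stronger readings are not supported:

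- A reader might infer that the vital-sign tables must show nothing whether or not the drug has an effect. That covers only effects gone before the visit, and adverse-event reports or unscheduled ECGs could still show one.
- A reader might infer that a null table will be presented as proof of cardiovascular safety. Section 7.3.4 plans descriptive safety analyses with no hypothesis tests.
- A reader might infer that a planned pulse exposure-response analysis has been left without data. Sections 5.3.4 and 7.3.5 name efficacy response and adverse events, not pulse.

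**What to change.** **Protocol**
- State in the Flow Chart that Visit 2 vital signs are taken before the dose.
- Add one seated pulse and blood-pressure reading just before the 0:45 PK sample, in all three arms, so that placebo controls for the visit and the blood draw. A reading at 1:30 is optional.
- Qualify Sections 5.6 and 1.4: later clinic vital signs and ECGs are not timed to peak exposure.

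**SAP**
- Label the pre-dose and post-dose Visit 2 readings as separate time points.
- Summarise change from the pre-dose Visit 2 value by arm, as a stated exception to the Visit 1 baseline in Section 6.7.
- Exempt these readings from the latest-measurement rule in Section 7.8.3. Otherwise the post-dose value would replace the pre-dose one.

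**Cost.** A few minutes per patient within a stay that already exceeds two hours, one set of eCRF fields and one summary table. No extra blood draw is needed.

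**Limit.** SAP Section 4 records that recruitment stopped early, so the yield is below the planned 387 patients. For patients already past Visit 2, the added reading is no longer possible. What remains is to correct the wording and to state the limitation in the trial report.

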## 6. INVESTIGATIONAL PLAN

### 6.1 VISIT SCHEDULE

All patients are to adhere to the visit schedule as specified in the [Flow Chart](#). If any visit needs to be rescheduled, subsequent visits should follow the original visit date schedule by referring to the date of randomisation (Visit 2).

### 6.2 DETAILS OF TRIAL PROCEDURES AT SELECTED VISITS

Study procedures to be performed at each visit are listed in the [Flow Chart](#). Additional details regarding visit procedures are provided in [Section 5](#) and below.

The members of the site staff that will be administering the assessments have to be properly trained (either at the investigator meeting or individually), and training documentation must be filed in the ISF. It is the responsibility of the Principal Investigator at the site to ensure proper training of all members of the site staff involved in the assessments.

#### 6.2.1 Screening Period

No trial procedures should begin until the patient has signed the informed consent. After a patient has signed the informed consent, the patient is enrolled in the trial and has begun screening. The patient should be recorded on the enrolment log and be registered in the IRT as a screened patient. The Screening procedures are not required to be completed on the same day.

Additional written informed consent for the unspecified pharmacogenomics sample must be obtained if the patient is willing to provide the blood sample for DNA banking.

Patients who have a laboratory test value outside the range that would jeopardize patients' safety while participating in this clinical trial may have the test repeated once to determine eligibility; however, the result must be available prior to Visit 2 (Day 1). The site should inform the authorized monitors (CML/Clinical Research Associate (CRA)) of their intent to redraw a sample(s) and receive the approval from the CML before they send out the retest sample to the central laboratory.

Patients who are not eligible for randomisation should be entered as a screen failure in IRT.

Patients who failed screening may repeat the screening phase once after discussion between the investigator and sponsor, providing the reasons for screening failure were reversible and have been resolved. Permission to rescreen patients must be obtained from the TCM or CML, and documentation of approval filed in the ISF. The patient who will be rescreened needs to be re-consented and be given a new patient number. All the study procedures for the Screening Visit (Visit 1) must be repeated upon rescreen.

## 6.2.2 Treatment period(s)

Eligible patients will be trained and set-up with the smartphone medication adherence monitoring Platform at Visit 2 prior to taking their first dose of study drug. Please refer to the manual in the ISF.

Study medication will be allocated via IRT and dispensed at visits specified in the [Flow Chart](#). Patients will be assigned a new medication number(s) at each of these visits. The first dose of study drug will be administered at the site after all baseline assessments have been completed and trial eligibility confirmed at Visit 2.

See Sections [5.3.2](#) and Section [10.3](#) for the sampling methods and time schedule for PK blood sampling.

Phone Visits are to be conducted at the time points specified in the [Flow Chart](#) to assess the overall status of the patient, assess suicidality, check compliance, and to collect new AE and concomitant medication information. If symptom worsening is suspected, an unscheduled in-clinic visit should be scheduled to further assess the patient for relapse. During the unscheduled visit, information should be gathered to determine whether any criteria for relapse have been met. PANSS and CGI-S should be assessed, as well as any other assessments necessary to assess the patient's condition, in the judgment of the investigator.

### Relapse of Schizophrenia

If the criteria for relapse (See [Section 2.1.2](#)) have been met, additional treatment considered necessary for the patient's welfare may be given. The patient may continue in the trial at the discretion of the investigator.

A blood sample should be collected at the time relapse is diagnosed to measure for detectable levels of antipsychotic medication.

